11.0 STATISTICAL CONSIDERATIONS

11.1 Study Design/Study Endpoints and Data Assessment Plan

Pazopanib with a low fat diet is a pilot study with a primary endpoint of feasibility and safety.

The primary outcome will be a description of toxicity and feasibility with the following endpoints: any hematologic toxicity of grade 4 or non-hematologic toxicities of grades 3 and 4 (excluding alopecia, and also excluding nausea and vomiting if the symptoms were manageable with standard care or antiemetic therapy); frequency and proportion of toxicities of all grades according to the CTCAE version 4.0 criteria; the frequency of dose reductions; the duration of treatment and the mean (or median) total dose taken. Each endpoint will include a 95% confidence around the reported statistic. Examples of exact confidence interval ranges with a sample size of 16 are presented in table 3.

Table 5:

| Frequency | Proportion | 95% Confidence Interval |
|-----------|------------|-------------------------|
| 1 | 6.25% | 0.2%, 30.2% |
| 2 | 12.5% | 1.6%, 38.4% |
| 3 | 18.75% | 4.1%, 45.7% |
| 6 | 37.5% | 15.2%, 64.5% |
| 8 | 50% | 24.7%, 75.4% |

The secondary objectives include overall response proportion by RECIST 1.1 including complete response and partial response at 12 weeks after start of pazopanib therapy start (CT chest, abdomen and pelvis). Each response proportion will be expressed with 95% exact binomial confidence intervals.

The pharmacokinetic data (Cmax in units of ng/mL and the trough concentration in units of micro g/mL) will be reported in context of known PK data of pazopanib administered in the fasting state⁷ and described in the context of the toxicity data.

An interim safety analysis will be conducted after 8 patients have been treated for 2 cycles on pazopanib with a low fat meal. If greater than 5 patients of the 8 experience hematologic toxicity of grade 4 or non-hematologic toxicities of grades 3 or 4 (excluding alopecia, and also excluding nausea and vomiting if the symptoms were manageable with standard care or antiemetic therapy), the study will be pause. Further study may be continued with an amendment to decrease the starting dose to 200 mg PO daily with low fat meal subject to PRC review/approval and IRB review/approval.

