| 
Study Product(s), Dose, Route, Regimen
 | 
Pazopanib 400mg (starting dose) PO daily with low-fat meal (LFM) in 14 day cycles. Pazopanib may be increased to 600 mg and subsequently to 800 mg PO with low-fat meal daily starting with second cycle if the prior dose is tolerated. Pazopanib may be decreased to 200 mg PO with low-fat meal daily starting with second cycle if the starting dose is NOT tolerated. Pazopanib dose may be adjusted every 2 weeks based on toxicities. No re-escalation of dose is allowed.
 |
| 
Duration of Administration
 | 
Until progression of disease or unacceptable toxicity or withdrawal from protocol therapy or after 6 cycles (12 weeks) of Pazopanib treatment.
 |
| 
Statistical Methodology
 | 
The feasibility and safety of Pazopanib with low-fat meal will be assessed based on the following statistics with a 95% confidence interval around the reported statistic: frequency of toxicity, severity of toxicities (according to CTCAE version 4.03 criteria), frequency of dose-reductions, duration of therapy, and mean or median total dose taken.
 |

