1.3 Study Design/Schema

Registered subjects will take pazopanib by mouth with a low-fat meal (**containing less than 400 calories and less than 20% fat or 10 grams per meal**) approximately, some sample meals are described in appendix 1) every day in 14 day cycles, for a total of 6 cycles, with a starting dose of 400 mg and adjusted for the next cycle (dose level +1: 600 mg; dose level +2: 800 mg; dose level -1: 200 mg) based on toxicity assessment during or at the end of each cycle. No dose re-escalations are permitted. Imaging will be performed post 12 weeks of treatment.

An interim analysis for safety will be performed after 8 subjects have completed at least 2 cycles (4 weeks) of therapy.

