5.0 TREATMENT PLAN

5.1 Treatment Dosage and Administration

Protocol treatment must start within seven business days of registration to the study.

Subjects will take starting dose of pazopanib 400 mg PO once a day with a low-fat meal as specified in the protocol once daily in every 14 days cycles, for a maximum of 12 weeks.

Consecutive doses should be taken approximately 24 hours (\pm 4 hours) apart.

If the subject does not develop significant toxicities as described in Section 5.2 after the first cycle, then the pazopanib dose will be escalated to 600 mg PO once daily with low-fat meal for the next cycle. If the subject does not develop significant toxicities as described in Section 5.2 at 600 mg, then the pazopanib dose will be escalated to 800 mg PO once daily with low-fat meal for the next cycle.

Subject will be assessed for significant toxicities as described in section 5.2 at the end of each cycle by clinical exam and laboratory values including liver function tests. Any grade 3 or 4 pazopanib-related (as assessed by treating investigator) non-hematological toxicities (except specific toxicities listed in table 2, 3 and 4) will necessitate dose reduction by 1 dose level for the next cycle.

No dose re-escalations are permitted.

Table 1 Pazopanib Dose Levels in Study

| Dose Level | Pazopanib with low fat meal |
|------------|-------------------------------------|
| +2 | 800 mg daily |
| +1 | 600 mg daily |
| 0 | 400 mg daily (starting dose) |
| -1 | 200 mg daily |

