9.0 DRUG INFORMATION

9.1 Pazopanib

- Brand name: Votrient
- Description: 200 mg capsule-shaped, gray tablets dispensed in bottles with 120 tablets.
- Classification: Inhibitor of multiple tyrosine kinases
- Mode of action: Inhibition of VEGFR (vascular endothelial growth factor receptor), PDGFR (platelet derived growth factor) and c-kit,
- Pharmacokinetics: Pazopanib is routinely administered without food i.e. at least 1 hour before or 2 hours after a meal (https://www.gsksource.com/pharma/content/dam/GlaxoSmithKline/US/en/Prescribing_Information/Votrient/pdf/VOTRIENT-PI-MG.PDF). When thus administered WITHOUT food, pazopanib has a median absolute bioavailability of 21% and mean half-life of 30.9 hours. The median time to peak concentration is 2-4 hours after dose, and repeated daily dosing results in 1-4 fold increase in AUC and Cmax with a daily dose up to 800mg daily. Doses above 800mg daily did not show a consistent increase in AUC and Cmax. Administration with food results in about 2 fold increase in AUC and Cmax. Crushing the tablet also resulted in increased AUC, increased Cmax and decreased Tmax when compared to administration of the tablet as a whole. Based on these observations, it was recommended that pazopanib be administered as a whole tablet 1 hour before or 2 hours after a meal. Additionally, the bioavailability of pazopanib is affected by drugs that increase gastric pH, such as esomeprazole, resulting in reduce plasma concentration of pazopanib.

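### The only numeric study-level safety rule is applied once, after 2 cycles in 8 patients, so it requires no data at 800 mg

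*Combined protocol and SAP*

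**What the plan says.** The interim look is defined in section 11.1: "An interim safety analysis will be conducted after 8 patients have been treated for 2 cycles on pazopanib with a low fat meal". The pause condition follows: "If greater than 5 patients of the 8 experience hematologic toxicity of grade 4 or non-hematologic toxicities of grades 3 or 4", with alopecia and controllable nausea or vomiting left out. Section 1.3 words the timing as a minimum: "An interim analysis for safety will be performed after 8 subjects have completed at least 2 cycles (4 weeks) of therapy". The synopsis and section 11.2 describe the same single look. Section 8.8, on stopping rules, only refers the reader to section 11. If the study pauses, the one continuation route named in section 11.1 is an amendment to the starting dose.

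The dosing scheme is in sections 1.3 and 5.1. Treatment is given "every day in 14 day cycles, for a total of 6 cycles, with a starting dose of 400 mg". If cycle 1 is tolerated, "then the pazopanib dose will be escalated to 600 mg PO once daily with low-fat meal for the next cycle". If 600 mg is tolerated, "then the pazopanib dose will be escalated to 800 mg PO once daily with low-fat meal for the next cycle". The synopsis sets the treatment period: "Until progression of disease or unacceptable toxicity or withdrawal from protocol therapy or after 6 cycles (12 weeks) of Pazopanib treatment".

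Section 12 provides for review by the study's own monitoring committee at least quarterly and for quarterly reports to an independent board. It gives no numeric threshold. Sections 5.1 and 5.2 set dose reductions for individual patients.

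**The concern.** Safety is part of the primary objective, and the reason for caution is the effect of food on exposure. Section 9.1 states: "Administration with food results in about 2 fold increase in AUC and Cmax". Section 1.1 adds that it is not known whether this carries over to repeated daily dosing with food. On the protocol's own account, sustained dosing at 800 mg with food is therefore the least characterised part of the scheme.

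The rule's minimum exposure ends just before that part begins. At that minimum, the study calendar in section 6.4 also has no scheduled post-baseline echocardiogram or urine protein/creatinine ratio, since both come at end of treatment.

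The study could thus pass its only numeric check without any 800 mg data having been required, and nothing brings the rule back later. Because the counting window is not defined, two analysts could also reach different counts from the same 8 patients.

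**Working it through.** **1. The plan's own figures.** The only computed figures in section 11.1 are exact 95% intervals for 16 patients. The Clopper-Pearson limits are the 0.025 quantile of Beta(x, 17 − x) and the 0.975 quantile of Beta(x + 1, 16 − x). They give 0.16–30.23% for 1 event, 1.55–38.35% for 2, 4.05–45.65% for 3, 15.20–64.57% for 6 and 24.65–75.35% for 8. All agree with the printed table within 0.1 percentage point. No operating characteristics are given for the pause rule.

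**2. Exposure the look requires.** Two cycles are 2 × 14 = 28 days. For a tolerating patient these are 14 days at 400 mg, 14 days at 600 mg and 0 days at 800 mg. The earliest 800 mg day is day 29. The remaining 6 − 2 = 4 cycles, or 8 of 12 weeks, lie beyond the required window.

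**3. Exposure the look would probably have.** Section 11.2 plans 16 patients over 12 months. With even accrual that is 52/16 = 3.25 weeks per patient. When patient 8 reaches week 4, patient k is 4 + 3.25 × (8 − k) weeks from start:

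| Patient | 1 | 2 | 3 | 4 | 5 | 6 | 7 | 8 |
|---|---|---|---|---|---|---|---|---|
| Weeks from start | 26.75 | 23.5 | 20.25 | 17.0 | 13.75 | 10.5 | 7.25 | 4.0 |

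Patients 1 to 5 would be past 12 weeks, patient 6 in cycle 6 and patient 7 in cycle 4. Suppose all 8 tolerate every step and have no holds. The scheduled time at 800 mg is then 8 × 8 = 64 patient-weeks. Of this, 5 × 8 + (10.5 − 4) + (7.25 − 4) + 0 = 49.75 patient-weeks would have passed at the look. If instead all 8 started together, the figure would be 0 of 64. The documents allow either case.

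**4. Chance of a pause.** More than 5 of 8 means at least 6. With true event rate p,

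P(pause) = 28p⁶(1 − p)² + 8p⁷(1 − p) + p⁸.

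At p = 0.5 this is (28 + 8 + 1)/256 = 37/256 = 14.5%. The documents give no composite event rate, so the rates below are assumptions.

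| Assumed rate within the counted window | 30% | 40% | 50% | 60% | 70% |
|---|---|---|---|---|---|
| P(pause) | 1.1% | 5.0% | 14.5% | 31.5% | 55.2% |

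If, say, the rate were 30% by week 4 and 60% by week 12, the same threshold would pause the study with probability 1.1% on 4-week data and 31.5% on 12-week data. If the rate hardly rises after week 4, the counting window makes little difference.

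**5. Whether a second application would come in time.** With even accrual, patient 8 starts at 7 × 3.25 = 22.75 weeks and reaches 12 weeks of treatment at 22.75 + 12 = 34.75 weeks. Patients 9, 10 and 11 start at 26.0, 29.25 and 32.5 weeks and would still be on treatment. Patient 12 would start at 35.75 weeks, so patients 12 to 16 would not yet have enrolled.

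**The case against.** The strongest reply is that nothing limits the count to cycles 1 and 2. The synopsis and section 1.3 make the timing a minimum, and section 8.2 collects adverse events from first treatment to 30 days after the last dose. Counting everything up to data cut-off is at least as natural a reading. On the planned accrual, 7 of the 8 would be past the earliest 800 mg day at the look. All of this stands. A reader might infer that the look will be made without 800 mg data, or that later events are excluded; the documents support neither. What remains is that later data are permitted but not required.

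A second reply is that the look serves the starting dose, the only thing the named continuation route would change, while toxicity after escalation is handled within each patient. That is a coherent purpose, but section 11.1 does not state it. A reader might also infer that patients 9 to 16 are treated without safeguards. They are not: dose reductions and committee and board review continue throughout. None of these has a study-level numeric trigger, which is a defensible choice in a descriptive pilot.

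Third, the twofold food effect comes from single-dose comparisons, so exposure on daily dosing at 800 mg with food is unknown rather than known to be doubled. Only patients who tolerated 400 mg and 600 mg are scheduled to reach 800 mg, so late event rates may be modest.

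Finally, a second look at the same 8 patients adds little if accrual is even and later events are already counted: 64 − 49.75 = 14.25 patient-weeks, from patients 6 to 8. If accrual is fast it adds more, but patients 9 to 16 may then have enrolled already, because no hold on accrual is stated.

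**Conclusion.** The point holds in a limited form. The study's one numeric safety rule is applied once, at an exposure that includes no required time at 800 mg. Its counting window is undefined and it is not repeated. Depending on accrual, between 0 and 49.75 of 64 scheduled patient-weeks at 800 mg in the first 8 patients would have passed at the look, assuming full tolerance and no holds.

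The effect on the chance of a pause depends on how far the event rate rises after week 4, and the documents say nothing on that. Over assumed rates of 30% to 70% the chance runs from 1.1% to 55.2%. No single pair of early and late rates should be read as the size of the gap.

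This is a worthwhile improvement to safety monitoring. It does not show that the design is unsafe.

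**What to change.** In section 11.1, keep the threshold and the 2-cycle look, and add two sentences:

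1. The count includes every qualifying event in those 8 patients from first dose to the data cut-off of the analysis, in whatever cycle it occurred.
2. The same rule is applied once more, when those 8 patients have all completed or left the 12-week treatment.

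Sections 5.1, 8.8 and 11.1 should also be reconciled on what exposure the rule covers. This includes the fact that the only continuation route named after a pause concerns the starting dose, whereas events counted later may arise at other dose levels. Any choice of dose or threshold is for the sponsor.

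The cost is protocol wording and one extra tabulation from data already collected. The chance of a pause goes up, and the rise may be material if late toxicity is common. The change protects later patients only through what is learned from the first 8; it does not count events in patients 9 to 16.

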8.8 Stopping Rules for the Study at Interim Analysis

- Please refer to section 11

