11.2 Sample Size and Accrual

A sample size of 16 patients with metastatic renal cell carcinoma will be enrolled over a 12 month period with an interim analysis for safety after 8 patients have completed 2 cycles. As a pilot study, this sample size is a convenience sample and sufficient to determine the feasibility of administering pazopanib with a low-fat meal in advanced renal cell carcinoma, the associated toxicity profile and preliminary efficacy measures such as ORR, PFS or overall survival.

Based on data from this pilot study, a larger follow-up study may be warranted to definitively address the cost savings of administering pazopanib with low fat meal and the efficacy of the drug when given with low fat meal.

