12.0 DATA AND SAFETY MONITORING

This trial will be monitored in accordance with the NCI approved University of Michigan Comprehensive Cancer Center Data and Safety Monitoring Plan. The study specific Data and Safety Monitoring Committee (DSMC), consisting of the protocol investigators, data manager or designee, and other members of the study team involved with the conduct of the trial, will meet quarterly or more frequently depending on the activity of the protocol to provide continuous review of the data and patient safety. The discussion will include matters related to the safety of study participants (SAE/UaP reporting), validity and integrity of the data, enrollment rate relative to expectations, characteristics of participants, retention of participants, adherence to the protocol (potential or real protocol deviations) and data completeness. At the regular DSMC meetings, the protocol specific Data and Safety Monitoring Report form will be completed. The report will be signed by the Principal Investigator or by one of the co-investigators. Data and Safety Monitoring Reports will be submitted to the University of Michigan Comprehensive Cancer Center Data and Safety Monitoring Board (DSMB) on a quarterly basis for independent review.

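### The interim pause rule is read only at one fixed look, so the plan permits new patients to start after a sixth qualifying toxicity has already decided the pause

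*Combined protocol and SAP*

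**What the plan says.** Section 11.1 sets the timing, "An interim safety analysis will be conducted after 8 patients have been treated for 2 cycles on pazopanib with a low fat meal", and the condition, "If greater than 5 patients of the 8 experience hematologic toxicity of grade 4 or non-hematologic toxicities of grades 3 or 4", with exclusions for alopecia and for manageable nausea and vomiting. If the condition is met, the study pauses. Section 1.3 gives the same timing, "An interim analysis for safety will be performed after 8 subjects have completed at least 2 cycles (4 weeks) of therapy", as does section 11.2, "with an interim analysis for safety after 8 patients have completed 2 cycles"; the synopsis agrees. Section 8.8, headed "Stopping Rules for the Study at Interim Analysis", only points to section 11.

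Until a pause, section 5.1 governs each new patient: "Subjects will take starting dose of pazopanib 400 mg PO once a day with a low-fat meal". The starting dose can change only after the pause, subject to PRC and IRB approval: "Further study may be continued with an amendment to decrease the starting dose to 200 mg PO daily with low fat meal".

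Other oversight is in section 12. The study-specific committee, made up of the investigators and study team, "will meet quarterly or more frequently depending on the activity of the protocol to provide continuous review of the data and patient safety", and the centre's monitoring board receives quarterly reports for independent review. Neither is tied to the 6-of-8 threshold or to a halt in accrual. No section says whether accrual continues while the first 8 complete 2 cycles.

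**The concern.** The rule counts patients with an event among a fixed group of 8. Once six have had one, the other two cannot bring the count back to five. The look can then only confirm a pause, but the plan ties the pause to the look, which waits for completed cycles. In the meantime, any of patients 7 and 8 not yet started may start and, if accrual goes on, so may patient 9.

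This concerns when the rule is read, not where the threshold lies. Safety is part of the primary objective. Section 1.1 reports roughly a twofold rise in Cmax and AUC with food, and says it is unclear whether this carries over to repeated daily dosing. The delay is longest when the true toxicity rate is high, which is the case the rule exists for.

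**Working it through.** **Plan's own figure.** None exists for this rule: the documents give no target rate, error rate or pause probability. The nearest stated figures, the exact 95% intervals for n = 16 in section 11.1, reproduce to within 0.1 percentage point but do not bear on timing.

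**Inputs from the documents**
- Accrual: 16 patients in 12 months (11.2), so one every 365/16 = 22.8 days.
- Look: 8 patients with 2 cycles, 4 weeks or 28 days (1.3, 11.1).
- Pause: more than 5 of 8, so at least 6 (11.1).

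**Assumptions not in the documents**
- True rate p of qualifying toxicity per patient.
- Even spacing of starts.
- Event times uniform over each patient's first 28 days.
- The 8 are the first 8 patients treated.
- Accrual is not held.

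**Step 1: calendar.** Patient 8 starts on day 7 × 22.8 = 160 and the look falls on day 160 + 28 = 188. Patient 9 starts on day 8 × 22.8 = 182.5, about five days before the look.

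**Step 2: chance of a pause.** P(X ≥ 6) with X binomial(8, p), if all events fall within 28 days.

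**Step 3: delay and new starts.** Simulate the time of the sixth qualifying patient among the first 8. Where this falls by the look, count the patients who start between it and the look.

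| True rate | P(pause) | Mean delay, days | Mean new starts, given pause | Of these, up to patient 8 | Mean new starts per trial, unconditional |
|---|---|---|---|---|---|
| 40% | 5.0% | 25 | 1.3 | 0.4 | 0.06 |
| 50% | 14.5% | 26 | 1.4 | 0.5 | 0.2 |
| 60% | 31.5% | 29 | 1.5 | 0.6 | 0.5 |
| 80% | 79.7% | 38 | 1.9 | 0.9 | 1.5 |
| 90% | 96.2% | 47 | 2.3 | 1.3 | 2.2 |

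The last column is P(pause) times new starts given a pause: at 60%, 0.315 × 1.47 = 0.46; at 80%, 0.797 × 1.87 = 1.49. The fourth column exceeds the fifth by about one, which is patient 9.

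**Step 4: sensitivity, given a pause**
- Poisson accrual at the same rate: 1.1, 1.2, 1.7 and 2.0 new starts at 50, 60, 80 and 90%.
- Accrual completed in 6 months: about 1.8 to 2.6 at 60–90%. Counting only patients up to number 8: 0.3 at 60% and 0.5 at 80%.
- Events spread over 84 days, 12-month accrual: 1.2 to 1.5 at 60–90%.

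**Step 5: does earlier reading change the chance of pausing?** Let T be the time of the sixth qualifying patient among the 8, and L the time of the look. The count at L is at least 6 exactly when T ≤ L. A trigger that fires at T, and only up to L, therefore pauses exactly the trials that the look would pause, whatever the event timing. Without that end point the two rules differ. With events over 84 days and a rate of 80%, six events have occurred by the look in 50.3% of trials but occur eventually in 79.7%.

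**The case against.** The strongest reply is that a single fixed look is a legitimate choice in a 16-patient, single-centre, open-label convenience pilot with real oversight between looks. The principal investigator hears of every serious adverse event within 1 business day (8.5), section 12 provides committee and board review, the university can terminate the study (5.7), and monitoring follows an institutional plan that is not reproduced here. This stands in part. A reader might infer that patients will keep being started with no safeguard; the documents do not support that. They permit further starts, and a halt is left to discretion. But no section obliges anyone to act when the plan's own number is reached, and a mean delay of 25 to 47 days can fall wholly between quarterly meetings.

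Second, a reader might infer that accrual is stated to continue up to the look. The protocol is silent. About one of the counted starts is patient 9, which depends on that silence and on exact even spacing. The count up to patient 8 is the safer lower figure.

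Third, the wording counts patients treated for, or having completed, 2 cycles. If those who stop early do not count, a sixth event among the first 8 starters does not settle the result. That is a fair limit. However, section 5.2 makes anyone with one dose evaluable for toxicity, which favours counting the first 8 dosed.

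Fourth, figures conditional on a pause can mislead: per trial, the gain is only 0.06 to 0.5 patients at rates of 40–60%. That also stands, and both sets are shown.

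**Conclusion.** The point holds as a gap in what the plan requires. The threshold is attached to one look, nothing applies it sooner, and further patients may start after the outcome is settled. When a pause occurs, the size is about 1.4 to 2.3 patients of 16 at true rates of 50–90%, or 0.5 to 1.3 counting only up to patient 8. Averaged over all trials it is about 0.06, 0.2, 0.5 and 1.5 at 40, 50, 60 and 80%. These figures rest on the assumed accrual pattern, event timing and definition of the 8. No expected rate of qualifying toxicity is given, so none of the rows can be singled out as the likely one.

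It would go too far to say that any running version of the rule leaves the chance of pausing untouched. That is true only if the early trigger ends at the look and the same 8 patients are counted. Nor does this point show that the threshold is wrong.

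**What to change.** In section 11.1, keep the threshold. State that the 8 are the first 8 patients who receive at least one dose, including any who stop early, and add:

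> *If, at any time up to the interim analysis, a sixth of these 8 patients has a qualifying toxicity, the study is paused then, without waiting for all 8 to complete 2 cycles; otherwise the interim analysis takes place as planned.*

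Mirror this in the synopsis and in sections 1.3 and 11.2. The same edit should say when the look falls if one of the 8 stops before 2 cycles, and whether accrual continues up to the look.

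No extra patients are needed. The cost is a running count of events already recorded, with prompt adjudication of the nausea and vomiting exclusion. If a pause occurs, the amendment is written on slightly fewer treated patients.
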